3.3.4 Protocol for Limb volume assessment

Weight gain during pregnancy is well known. This occurs not only due to fetal growth and uterus enlargement, but also due to water retention and increased blood volume which are required for fetal circulation. This excessive water retention especially in the third trimester is coupled with accumulated fat cause swelling (oedema) especially in both lower limbs. Therefore, measuring limb volume during pregnancy is considered significant to estimate water and fat amounts gained during pregnancy and correlate these findings with potential VV incidence. This proposed study will assess the lower limb volume based on girth measurements using Truncated cone method. This method has the advantage of measuring bilateral limb volume oedema where no comparator (unaffected) limb is available. This method measures limb volume by manual perimetry using tape measure to find limb circumference. Tape measure tension may be inconsistent which can change the limb circumference measurement by up to 3% (Cheah *et al.*, 1989). Therefore, this study will use spring-loaded controlled tension device to keep the tape in closer contact with the skin without compressing the underlying tissue.

Measurements will be taken while the patient is standing. Circumferences will be measured every 10 cm from the sole up to the seventh measurement. A single researcher will measure all patients to prevent differences in tension on the tape. The data will be processed using the truncated-cone formula (Campanholi, Duprat Neto and Fregnani, 2011):

$$V = h (C1 \times C2 + C1^2 + C2^2) / 12\pi$$

V: Volume of each segment (final segment of the limb).

C1 and C2: Circumference measured between the points (at either end of each segment length)

H: Distance between the circles (C1 and C2 in each segment), measured in centimetres.

Total limb volume: is determined by the sum of the segment volumes.

Finally, Patient will be asked to rest and take a seat on a chair, circumferential measurements will be entered into computer software programmes or pre-programmed calculators to calculate limb volume of each recruited patient.

3.3.5 Protocol for Iliac vein compression test (venous outflow function)

This proposed study will examine iliac vein compression (venous outflow function) in pregnancy using photoplethysmography (PPG) technique. This is due to the difficulty of examining iliac veins using ultrasound in pregnancy due to increased size of gravid uterus. Large size of gravid uterus in pregnancy causes iliac veins compression which makes iliac veins hard to investigate. PPG is a non-invasive method used to evaluate the severity venous reflux by measuring the venous refilling time (VRT). VRT is considered to be abnormal when the refilling time is measured (less than 20 seconds). PPG technique has low specificity compared to other imaging tests and it is considered not accurate in locating the areas of reflux. However, alongside with its capability of evaluating the degree of reflux, it can also predict the treatment outcomes (Cheng and Wong, 1995).

The principal of PPG works by using a small light source and a photoelectric cell attached to the skin. Produced light will transmit the skin and will be scattered by the tissue and partially absorbed. Scattered light will emerge out passing the skin to be detected by photoelectric cell. Photoelectric cell will be attached on the side or opposite the source of light to monitor blood perfusion based on transmission and reflection modes. Following this, the intensity of the light signals detected by photoelectric cell will be converted to PPG signals.

In this proposed study, patient will be seated with her both legs dangling on the floor. PPG sensor will be attached to the patient's skin in the medial supramalleolar area of the leg (the distal lower medial area of the leg). The exam will start by asking the patient to flex and extend one foot (five times), while the other foot placed on the floor.

Following this, a traced graph will appear on the machine's screen. When the trace is stable, it means that it is the end of the VRT. The exam will be repeated to evaluate the filling time of the second leg. All measurements will be recorded immediately.

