1.1 Background

Varicose veins (VV) are the early sign of Chronic venous insufficiency (CVI) which are characterised by abnormal tortuosity and dilatation of superficial veins of lower limb extremities (Naoum *et al.*, 2007). Symptoms of VV are variable and depend on the stage and severity of disease. In early stages, symptoms of VV include pain, leg heaviness and mild swelling (Adhikari *et al.*, 2000). As the disease advances, symptoms include skin changes such as pigmentation, lipodermatosclerosis and ulceration (Kendler *et al.*, 2010; Shadrina *et al.*, 2018). Pregnancy is an established risk factor for the development of VV (Ismail *et al.*, 2016). Three main hypotheses for this observation have been proposed. First, it was hypothesised that increased size of gravid uterus during pregnancy may result in increased venous pressure on iliac veins resulting in a disruption of lower limb venous outflow (Mashiah *et al.*, 1991). However, VV may develop in the first trimester before the onset of these mechanical factors (Dindelli *et al.*, 1993). Secondly, pregnancy results in an increased blood volume which may lead to elevated pressure in lower limb vasculature (Ismail *et al.*, 2016). Both theories suggest that high pressures may result in venous valve impairment (Bergan *et al.*, 2006). Thirdly, VV in pregnant women were found to be associated with increased estrogen and progesterone levels (Mashiah *et al.*, 1991; Ortega, Asunsolo, Alvarez-Rocha, *et al.*, 2018). Estrogen hormone elevates coagulation protein levels which cause thrombosis. Additionally, estrogen dilates venous valves due to its role in relaxation and releasing the chains between collagen fibers. On the other hand, progesterone prevents smooth muscle contraction which therefore increases valvular insufficiency due to vasodilation which causes lack of connection between two valves (Ropacka-Lesiak, *et al.*, 2012). Moreover, large number of studies have discussed the associated risk factors that contribute to VV development. However, there are lack of studies that consider VV risk factors and pathophysiology in pregnant women. Understanding the aetiology of VV in pregnancy may allow us to better identify those at risk and manage this risk accordingly.

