1.2 Rationale for current study

Regardless of the underlying pathophysiological cause, VV may have a negative social impact on patient's life and negative economic impact on health care budget. VV if left untreated can progress to late stages of chronic venous insufficiency (CVI) which include skin changes and ulceration (Adhikari *et al.*, 2000). Ulcers lower patient's quality of life and may result in social isolation, depression, reduce the ability to work and patients will be dependent on others (Evans *et al.*, 1994; Cesarone *et al.*, 2002). Furthermore, venous disease is costly to manage for healthcare service. For example, the cost of managing chronic wounds caused by ulcers in the UK National Health Service (NHS) during 2005 to 2006 was estimated from 2.3 to 3.1 billion pounds which was equivalent to 3% of total UK health care budget (Posnett, J. and Franks, 2007). Interestingly, the cost was increased between 2012 to 2013 when cost was estimated at 5.3 billions of pounds annually which consume 4% of the total health UK health care budget (Guest *et al.*, 2015).

1.3 Research hypothesis:

The development of post-partum chronic venous insufficiency is predictable and caused by both mechanical and hormonal factors.

2 Study aim and objectives:

The primary aim of this proposed study is to better understand the pathophysiology of VV in pregnant women. This aim will be achieved by meeting the following objectives:

Primary objective:

To develop an antenatal test to predict the risk of developing VV post-partum.

Secondary aims:

1. To evaluate mechanical factors causing VV in pregnancy
2. To evaluate hormonal factors causing VV in pregnancy.
3. To determine whether lower limb pain during pregnancy is related to changes in lower limb venous system.

3 Methods

3.1 Study design:

A prospective longitudinal study will be undertaken to assess the development of VV among pregnant women. This study will follow up patients for one year, starting by following up pregnant women from the first trimester of pregnancy to the end of the second and third trimester. Last follow up will be performed three months after giving birth. Consequently, this proposed prospective study will be conducting four follow ups for each participant.

3.2 Recruiting pregnant women in their first trimester:

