Initially, patients will be approached by a member of the direct care team in the Maternity outpatients' departments in the following hospitals: West Middlesex hospital, Queen Charlotte's and Chelsea hospital and St Mary's hospital. This will be managed by experienced research professionals in the area of vascular surgery. If a patient is prepared to discuss their potential role in this research, then the researchers will discuss the study and recruitment details at the patient's convenience. Recruitment is completely voluntary and will not affect their routine care, this will be made clear during the discussion regarding the research, and again during the consenting process. Time will be made available for any questions and for the patient to consider recruitment in their own time. Patients will be required to consent before any study-related procedures are carried out. Then her personal identifiable data will be coded and pseudonymised.

The recruited patient will be interviewed to obtain clinical information that is essential for robust analysis. This clinical information will include standard demographic form which will be used for all patients in each follow up in order to record and gather important information which represents the composition of the target population. Gathered data will include patients' details; patients name, day of visit, hospital name, ID number, date of birth. Furthermore, this demographic form will record potential risk factors which may associate with VV development such as race, number of

pregnancies, family history of venous disease, BMI which include weight and height, occupational factors, smoking, alcohol consumption and diet. Any complications arising from pregnancy will be also recorded (appendix 12.1). Finally, this proposed study will only record fetal weight in second and third trimester to correlate increased fetal weight with potential venous pathology.

First, patients will be asked to fill the demographic form then will be asked to stand on a scale to measure the weight. Height will be recorded by bringing the horizontal measure down to rest on the top of the participants head. Following this, patient will be asked to sit while measurements are recorded in a relevant source data sheet.

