Next, the patient will be asked to stand on a step facing the sonographer to assess the incidence of varicose veins using Duplex ultrasound (DUS) and vector flow imaging (VFI). While patient is standing, Truncated cone tool will be performed immediately by measuring leg circumferences in each segments of each limb to produce accurate measurements of lower limbs volume. Following this, patient will be asked to sit on a chair for perform Iliac vein compression test (venous outflow function) using photoplethysmography (PPG) technique. Finally, patient's quality of life assessment will be evaluated by using Aberdeen Varicose Veins Questionnaire (AVVQ) check list (Klem, Sybrandy and Wittens, 2009). Thereafter, the patient will be thanked for their participation and excused.

Clinical Laboratory tests will be managed and performed by experienced research professionals in the area of vascular surgery. Four appointments will be arranged for each patient to investigate DNA genomic testing and Estriol (E3) and progesterone hormonal testing. First appointment during first trimester will include both genomic DNA and hormonal blood tests. The three remaining appointments in the second trimester, third trimester and three months after giving birth will include hormonal blood samples only. Patients will be entitled to exit the study at any time without providing a reason, this is clearly stated on our information sheet and consent form. Verbal consent will be requested before all follow-up ultrasound scans.

Researchers will ensure that demographic data, ultrasound data, lower limb volume and iliac vein compression measurements, histopathological results and quality of life

assessment results will be collected and stored in such a way that confidentiality is preserved. All data will be pseudonymised by replacing names with research codes and by keeping any identifying information separate from the main dataset.

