3.3.2 Protocol for Duplex ultrasound scan (DUS)

All recruited pregnant women be scanned by duplex ultrasound scan (DUS) to investigate the evidence of VV. The examination will be bi lateral for each patient. The patient will be asked to remove their clothes to expose the lower limb from groin to ankle. Patient will be examined standing to evaluate valves competency against gravity. This is because veins are more dilated while standing which make it easier and more accurate to assess. This examination is considered intimate; therefore, a chaperone will be offered. The scan duration will take 30-45 min and patients may sometimes feel dizzy during the examination. To overcome this issue, patients will be asked to sit and take a rest during the examination.

There are two main techniques which will be applied to all venous segments. Firstly, B mode technique. B mode technique will be used to evaluate vein patency in transverse scan plane by observing the compressibility of veins to rule out any possibility of blood clots. Secondly, Spectral (Pulse wave) doppler technique will be used to evaluate venous flow characteristics (phasicity, spontaneity and direction flow) in longitudinal scan plane by applying manual distal augmentation to assess the reflux duration. All scans and measurements will be performed on SuperSonic Imagine's Aixplorer ® ultrasound system. Following this, 9 MHz linear ultrasound probe will be placed on the patient skin over the venous blood vessel to be scanned, with the use of coupling gel between the skin and the probe.

The scan will start by evaluating the deep and superficial veins system. Firstly, deep veins will be assessed by scanning the Common femoral vein (CFV) at the groin for patency and flow. Any abnormality in CFV indicates iliac vein obstruction therefore iliac veins and inferior vena cava should be examined. The examination will be continued by scanning the length of femoral vein (FV) (proximal to distal), popliteal vein and calf veins. Any thrombus or incompetence (Incompetent veins are defined as a reflux time more than 0.5 seconds) will be recorded.

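### PPG is titled the iliac compression (outflow) test but yields a reflux measure, and no outflow variable is coded or analysed, so the iliac part of secondary aim 1 rests on indirect evidence

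*Combined protocol and SAP*

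**What the plan says.** Section 1.1 gives as its first mechanism that the gravid uterus may cause "increased venous pressure on iliac veins resulting in a disruption of lower limb venous outflow". Section 2 makes mechanical causes the first secondary aim: "To evaluate mechanical factors causing VV in pregnancy".

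The test assigned to this mechanism is PPG. Section 3.2 lists an "Iliac vein compression test (venous outflow function) using photoplethysmography (PPG) technique", and 3.3.5 repeats it: "This proposed study will examine iliac vein compression (venous outflow function) in pregnancy using photoplethysmography (PPG) technique". The reason given in 3.3.5 is that the enlarged uterus makes the iliac veins hard to examine by ultrasound.

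The same section then says that PPG grades reflux through VRT, abnormal below 20 seconds. The outcome table in 7.2 lists PPG as reflux severity by VRT and nothing else. Section 8.2 compares mean VRT by t test and gives a kappa between the PPG and DUS classifications.

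On the DUS side, 3.3.2 says that spectral Doppler "will be used to evaluate venous flow characteristics (phasicity, spontaneity and direction flow) in longitudinal scan plane". It adds: "Any abnormality in CFV indicates iliac vein obstruction therefore iliac veins and inferior vena cava should be examined". The DUS outcomes in 7.2 are patency, flow direction and peak reflux velocity.

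**The concern.** A measurement chosen to stand for a cause (obstructed outflow) is defined as a measure of the effect (reflux). If the study reports a VRT difference from a procedure titled as an iliac compression test, a reader could take it as support for the compression hypothesis. By the plan's own definition it would show only that reflux differs, which DUS is already there to assess.

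The research hypothesis in 1.3 names both mechanical and hormonal causes, so it matters which variables speak to which cause. Without a coded outflow variable, the iliac mechanism must be inferred from timing and from correlates of a growing uterus. Section 3.3.6 notes that progesterone is also highest in the third trimester and may act on the veins then. A late-pregnancy pattern taken alone therefore does not separate the two explanations.

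**Working it through.** **No stated figure bears on this point.** The plan quantifies nothing for PPG or outflow. Its one power figure (8.1: 91.27% for 0.25 against 0.10 with n = 70) does reproduce, with exact two-sided rejection at 10 or fewer or at 26 or more events. It has no link to this measurement.

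**Step 1. What PPG delivers, place by place.**
- 3.2 and the title and first sentence of 3.3.5: iliac compression, outflow function.
- 3.3.5, principle: reflux severity, through VRT.
- 3.3.5, manoeuvre: seated, five foot flexions and extensions, then timing until the trace is stable. This yields a refilling time; no emptying or outflow reading is described.
- 7.2: reflux severity by VRT.
- 8.2: mean VRT, and agreement with DUS.

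Only the label says outflow. The definition, the outcome and the analysis say reflux.

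**Step 2. Whether DUS supplies the missing variable.**
- Patency: B-mode is used to "evaluate vein patency in transverse scan plane by observing the compressibility of veins to rule out any possibility of blood clots". That is a clot check, not a measure of outflow or of compression from outside.
- Flow direction: coded antegrade or retrograde in 7.2, which reads reflux.
- Peak reflux velocity: reflux by name.
- Phasicity, spontaneity, and any iliac or inferior vena cava (IVC) finding: in the 3.3.2 procedure but absent from 7.2, 8.2 and 8.3. For the deep veins, 3.3.2 says that thrombus or incompetence (reflux over 0.5 s) will be recorded. The end of the DUS section says that all recordings are saved and entered for analysis, so raw material may exist, but no coding or threshold is given.
- 8.3, longitudinal factors: age, BMI, smoking, ethnicity, pregnancies and family history. There is no outflow term.

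Count: the distinct DUS and PPG outcome measures are patency, direction, peak reflux velocity and VRT. None of the four is defined as outflow. Vector flow imaging repeats the first three.

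**Step 3. How many readings carry the label.** 2 legs × 4 visits = 8 PPG readings per woman at most; 8 × 70 = 560 in all at most.

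**Step 4. What a CFV sign could deliver.** This sizes the proposed addition, not the flaw. The frequencies and the odds ratio are assumptions; the documents give none for this sign. The unit is the woman at one visit, n = 70.

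Exact (Clopper-Pearson) 95% CI for the frequency of an abnormal sign:
- 7/70 = 10%: 4.1% to 19.5%
- 14/70 = 20%: 11.4% to 31.3%

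For the association with reflux, set the odds ratio to 3 and solve for the expected 2×2 cells a, b, c, d (sign and reflux, sign only, reflux only, neither). Then the 95% CI = exp[ln 3 ± 1.96 × √(1/a + 1/b + 1/c + 1/d)].
- Sign 10%, reflux 10%: cells 1.55, 5.45, 5.45, 57.55; SE 1.015; CI 0.41 to 21.9
- Sign 10%, reflux 25%: CI 0.61 to 14.8
- Sign 20%, reflux 10%: CI 0.58 to 15.6
- Sign 20%, reflux 25%: cells 6.08, 7.92, 11.42, 44.58; SE 0.633; CI 0.87 to 10.4

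With 20% lost (70 × 0.8 = 56 women), the first and last become 0.32 to 27.7 and 0.75 to 12.0. Every interval includes 1. Using both legs and four visits would narrow them by an amount that the documents do not let me state.

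**The case against.** The strongest reply is that the plan corrects itself. The outcome table calls PPG a reflux measure, 3.3.5 concedes its low specificity and that it cannot locate reflux, and nothing in section 8 equates VRT with compression. The risk of misreading therefore comes from a title and two sentences. This stands as a limit on the harm. It does not remove the contradiction, because 3.3.5 chooses PPG precisely as the substitute for iliac ultrasound.

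A second reply is that the DUS procedure already contains an outflow observation and that all recordings are kept. This also stands in part: a reader might infer that the study collects nothing on outflow, and the documents do not support that. What is missing is a coded, listed and analysed variable.

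Third, a reader might infer that secondary aim 1 cannot be addressed at all. That goes too far. The aim covers mechanical factors generally, and 1.1 names blood volume as well as iliac pressure. Limb volume is measured (3.3.4), and section 3.2 plans to "record fetal weight in second and third trimester to correlate increased fetal weight with potential venous pathology". Estriol and progesterone are measured at all four visits, so timing is not the only information available on hormones.

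Finally, a CFV sign is itself observational. Its value as a marker of partial compression rests on one unreferenced sentence in 3.3.2, and the scan is done standing. It would be closer to the hypothesis than VRT but would not by itself separate compression from hormones. That is why it is offered only as exploratory.

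**Conclusion.** The point holds in this form: VRT, as the plan defines and analyses it, is a reflux measure and cannot serve as evidence on iliac compression, and no outcome or analysis carries an outflow variable in its place. The iliac part of secondary aim 1 is left with indirect evidence: fetal weight, limb volume, and change across visits read alongside the hormone levels.

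This rests on the protocol's own wording and on no assumed number. The documents do not allow a bias to be sized, and the intervals above describe only the optional addition. The primary outcome and the sample size are unaffected. It should be corrected because, as written, a named mechanism would be reported through a test that the plan itself defines as measuring something else.

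**What to change.** 1. In 3.2, 3.3.5 and 7.2, describe PPG/VRT as a measure of reflux severity and drop the iliac compression and outflow title. State that VRT results will not be interpreted as evidence on iliac compression. This costs only wording; the study gives up presenting PPG as its compression test.

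2. As an exploratory addition, in 3.3.2 code CFV phasicity and spontaneity for each leg at each existing scan (for example normal, reduced or absent, at rest before augmentation), plus any iliac or IVC finding. Treat inadequate views as missing. List it in 7.2 as an exploratory outflow sign. In section 8, report its frequency at each visit and its association with DUS reflux over 0.5 s as an estimate with a 95% CI that accounts for repeated measures within a woman. Do not present it as a test.

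State as assumptions the grading scale, which is a proposal since the protocol has none, and the validity of the sign in a standing woman. The second step needs no new visit or procedure. It adds a few fields to the scan form and perhaps a little time to the 30 to 45 minute scan, because 3.3.2 describes Doppler with augmentation and does not mention a resting trace. If the team prefers not to add it, the first step alone removes the contradiction, provided the protocol also says that iliac compression is not directly measured.
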